Theoretical model for targeting both depression and smoking A recently proposed theoretical model⁵⁹ posits that among smokers with comorbid depression, adverse internal states of low positive affect (PA), high negative affect (NA) and cognitive impairment function as motivational states that predict greater reinforcement value of smoking and elicit an expectation of greater reinforcement value. Explicit goal-directed instrumental knowledge of response sequences that yield reinforcement from nicotine is acquired, which drives behavior to achieve the desired smoking outcome in specific external contexts. These incentive learning processes serve to promote smoking maintenance and relapse in depressed smokers. The theoretical framework is applicable to smokers in general. However, in those with comorbid depression, these internal motivational states are especially effective in driving smoking because depressed smokers experience more intense adverse states, thus greater reinforcement; and withdrawal is more severe, further intensifying these adverse states as smoking motivators. The high reward value of smoking in these states is particularly motivating during abstinence and is conceptualized as the primary trigger for smoking maintenance and relapse. A prediction of this model is that treatment should attenuate these states and reverse positive expectancies associated with smoking to help depressed smokers achieve cessation.

We posit that BA, given evidence of its efficacy in addressing depression and anxiety symptoms, will be more effective than HW at addressing these states and thus produce higher levels of smoking abstinence. More specifically, we hypothesize that BA will address PA through treatment components that increase availability of positive reinforcement and increase reward value of potentially pleasant events; NA through treatment components that encourage approach behavior in the context of adverse emotional states and encourage a problem-solving stance;^{60, 61} and cognitive deficits resulting from BA's greater resolution of depressive symptom severity.⁵⁹ We will evaluate PA, NA and cognitive function as mediators of both smoking and depression treatment outcomes.

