- 4) Have a lifetime or current diagnosis of Psychotic Disorder as assessed by specified Mini International Neuropsychiatric Interview (MINI) 7.0.2 modules.
- 5) Have a past or current diagnosis of Bipolar Disorder I or II or have a past or current diagnosis of Other specified Bipolar and related disorder as assessed by specified MINI 7.0.2 modules.
- 6) Any otherwise not specified medical or psychiatric condition, illness, disorder, or concomitant medication that could compromise participant safety or treatment, as determined by the Principal Investigator and/or Study Physician.
- 7) Participant considered by the investigator as unsuitable candidate for full participation in the study.

Refer to Table 1 & Table 2 (Prenatal & Postpartum) for the full schedule of assessments, and more details in section AIM 3 and AIM 4 Assessments.

Refer to sections Participant Recruitment (Aim 1, 3, 4), Pre-Screening Assessment (AIM 1, 3, 4), Informed Consent Process (AIM 1, 3, 4), Baseline Screening Phone Visit (AIM 1, 3, 4) for detailed information of the enrollment process.

Aim 4 Approach (Stage IB)

Design The objective of Aim 4 is to conduct a preliminary randomized trial to evaluate the effect of BA on abstinence and depression at 4 ½ months postpartum; to demonstrate the feasibility of the smartphone-delivered BA intervention for depressed pregnant smokers during prenatal and through 2 ½ months postpartum, and feasibility of study procedures. We will recruit pregnant smokers in the same manner as AIM 3 (Stage IA). We will employ a randomized, controlled between groups design in which depressed pregnant smokers will be randomly assigned, using a form of adaptive randomization called minimization,¹¹² to either BA or HW. We will stratify treatment assignment by baseline depression, smoking rate and gestational age. The data that are collected will be used to support feasibility of delivering a prenatal and postpartum intervention to depressed pregnant smokers via smartphone and to provide estimates of effect size for planning future fully-powered trials.

Participants We will recruit up to 50 depressed pregnant smokers who are between 18 to 32 weeks gestational age in their pregnancies.

Compensation AIM 4

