Examples of such medical events include allergic bronchospasm requiring intensive treatment in an emergency room or at home, blood dyscrasias or convulsions that do not result in inpatient hospitalization, or the development of drug dependency or drug abuse (21 CFR 312.32).

- Important medical events as defined above may also be considered serious adverse events. Any important medical event can and should be reported as an SAE if deemed appropriate by the Principal Investigator.

- All events occurring during the conduct of a protocol and meeting the definition of a SAE must be reported to the IRB in accordance with the timeframes and procedures outlined in "The University of Texas M. D. Anderson Cancer Center Institutional Review Board Policy for Investigators on Reporting Serious Unanticipated Adverse Events for Drugs and Devices".

- Serious adverse events will be captured from the time of the first protocol-specific intervention, until the last treatment visit, unless the participant withdraws consent. Serious adverse events must be followed until clinical recovery is complete and laboratory tests have returned to baseline, progression of the event has stabilized, or there has been acceptable resolution of the event.

It is the responsibility of the PI and the research team to ensure that serious adverse events are reported according to the Code of Federal Regulations, Good Clinical Practices, the protocol guidelines, the sponsor's guidelines, and Institutional Review Board policy.

STATISTICAL DESIGN AND POWER

We will employ a randomized, controlled between groups design in which 60 depressed pregnant smokers will be randomly assigned, using a form of adaptive randomization called minimization, to either Behavioral Activation (BA) or Health and Wellness (HW). We will stratify treatment assignment by baseline depression, smoking rate, and gestational age.

Data analyses will be conducted by our University of Texas Health Science Center collaborator [name]. [name] will be provided deidentified data from which to conduct the analyses and thus will not have access to participants' protected health information (PHI).

[figure not shown]
General Data Analytic Strategy: Bayesian Statistical Methods

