Conduct a preliminary randomized trial with depressed pregnant smokers comparing the BA to HW to evaluate the following: 1) The effect of BA on abstinence at 4 ½ months postpartum, which is a primary outcome. Logistic modeling will evaluate smoking abstinence, measured by biochemically verified TLFB, at 4 ½ months postpartum as a function of treatment group. **2) The effect of BA on depression at 4 ½ months postpartum, which is a primary outcome.** Generalized linear modeling will evaluate depression, measured by the PHQ-9, at 4 ½ months postpartum as a function of treatment group. **3) Feasibility of depressed pregnant smokers' acceptance of the smartphone delivery of BA and HW, and assessment components indicated by a) retention, which is a primary outcome, b) completion of prenatal and postpartum sessions, which is a primary outcome c) completion of study assessments, which is a secondary outcome d) strength of therapeutic alliance from both the participant and therapist perspective, which is a secondary outcome and e) participant and therapist ratings on satisfaction questionnaire, which is a secondary outcome.** Survival analysis will evaluate retention by modeling time to drop-out as a function of treatment condition. Binomial logistic modeling will evaluate the proportion of completed sessions as a function of treatment condition across the entire study as well as in the pre-natal and post-partum periods separately. Generalized linear models will evaluate participant and clinician measures of therapeutic alliance, measured by the WAI, as a function of treatment group. Similarly, generalized linear modeling will evaluate satisfaction as a function of treatment group. **4) Feasibility of study procedures as indicated by a) percentage of sessions interrupted by technical difficulties, which is a secondary outcome, and b) percentage of urine tests (cotinine and/or anabasine) received for biochemical verification of self-reported abstinence at 4 ½ months postpartum follow-up, which is a secondary outcome.** Binomial logistic models will evaluate the proportion of sessions interrupted for technical difficulties and the proportion of biochemically verified abstinence measures as a function of treatment. These analyses will provide estimates with 95% credible intervals for each of these proportions in each group that will permit assessment of feasibility.

Specific Analyses: Secondary Aim 1 (Stage IB)

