Evaluate change in hypothesized treatment mechanisms including positive affect, negative affect and cognitive impairment in relation to treatment effects on smoking and depression. It would be ideal to evaluate the change in positive affect, negative affect and cognitive impairment as mediators of treatment effects on 4 ½ month post-partum outcomes via structural equation modeling. Specifically, we could model the change over time in each mediator and evaluate the degree to which each growth factor might transmit the effect of treatment. However, it is possible that a sample size of N = 50 will not provide enough variability to estimate certain parameters implied by such a model (e.g. the slope of change in each of these mediators may have minimal variance and function poorly as a mediator). If this latter scenario obtains, we will evaluate each component of a mediational analysis in separate analyses to evaluate the evidence for mediation of treatment effects by positive affect, negative affect and cognitive impairment. Specifically we will: a) evaluate the change over time in each mediator as a function of treatment using multi-level modeling; b) Evaluate the effect of

treatment on the outcome (smoking cessation or depression); and c) evaluate the outcome (smoking cessation or depression) as a function of change in the mediator captured either through a difference score (six months – baseline) or residual change score (six months residualized on baseline). While the former (SEM) approach would provide a more elegant test of the overall model of behavior change, the latter may be necessary based on the properties of the sample.

PARTICIPANT SAFETY MONITORING PLAN

Assessment of Worsening Depression, Anxiety and Suicide Risk

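### The fallback mediation step permits a raw mediator difference score with no baseline terms, which would cut the mediator path by half or more if the outcome follows the later mediator level

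*Combined protocol and SAP*

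**What the plan says.** The section Specific Analyses: Secondary Aim 1 (Stage IB) prefers a structural equation model with growth factors as mediators. It foresees that this may fail: "it is possible that a sample size of N = 50 will not provide enough variability to estimate certain parameters". In that case three separate analyses replace it. Step (c) is to "evaluate the outcome (smoking cessation or depression) as a function of change in the mediator captured either through a difference score" or a residual change score. In full, the change is "captured either through a difference score (six months – baseline) or residual change score (six months residualized on baseline").

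The section does not say which score applies or when. It lists no baseline mediator, baseline PHQ-9 or treatment term for step (c).

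Three other places bear on this:

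- Under Specific Data Analyses: Aim 4, the depression outcome also has no baseline term: "Generalized linear modeling will evaluate depression, measured by the PHQ-9, at 4 ½ months postpartum as a function of treatment group".
- Under Bayesian Modeling Strategy, a baseline variable becomes a covariate only if the groups are found to differ on it and it correlates with outcome. Results are then reported with and without it.
- Under Aim 4 Approach, Design: "We will stratify treatment assignment by baseline depression, smoking rate and gestational age". A factor balanced by minimization is unlikely to show the group difference that the covariate rule requires.

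**The concern.** Step (c) sets the level of the outcome at follow-up against the change in the mediator from baseline. A raw difference is negatively related to its own baseline value. The plan's theory links that baseline value to depression: among those with comorbid depression, "depressed smokers experience more intense adverse states". If baseline depression also predicts follow-up PHQ-9, women who start worst tend to show the largest mediator improvement through regression to the mean and still end with the higher PHQ-9. That pulls the estimated path against the true one. Randomisation does not protect this link, because mediator change is not assigned.

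Residual change is uncorrelated with the baseline mediator by construction, so the two permitted scores can give different answers from the same data. Secondary Aim 1 is the trial's test of its own theory, and its answer could turn on a choice left open until the data are seen.

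**Working it through.** **No figure to reproduce.** The documents give no correlation, effect size or decision threshold for the mediation analysis. The inputs below are assumptions, except N = 50, which is in the Secondary Aim 1 section. (The section Statistical Design and Power says "60 depressed pregnant smokers will be randomly assigned"; N = 50 is used here because the fallback text uses it.)

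**Model.** Standardised variables, scored so that higher is worse. M0 and M1 are the baseline and follow-up mediator, with correlation κ. Y0 is baseline PHQ-9, with correlation r00 with M0, and is linked to M1 only through M0. The outcome is Y = b·M1 + g·Y0 + error.

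**Raw difference.**

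- Cov(Y, M1) = b + g·κ·r00
- Cov(Y, M0) = b·κ + g·r00
- Cov(Y, M1 − M0) = (1 − κ)(b − g·r00)
- Var(M1 − M0) = 2(1 − κ)
- Slope = **(b − g·r00)/2**

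**Residual change,** R = M1 − κ·M0.

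- Cov(Y, R) = b + g·κ·r00 − κ(b·κ + g·r00) = b(1 − κ²)
- Var(R) = 1 − κ²
- Slope = **b**

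Regressing Y on M1, M0, Y0 and treatment also returns b.

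**Expected raw-difference slopes.**

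| g | r00 | true b = 0 | true b = 0.35 |
|---|---|---|---|
| 0 | any | 0 | 0.175 |
| 0.4 | 0.4 | −0.08 | 0.095 |
| 0.5 | 0.5 | −0.125 | 0.05 |
| 0.5 | 0.6 | −0.15 | 0.025 |

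For example, (0.35 − 0.5 × 0.6)/2 = 0.025. The expected slope reverses only if g·r00 > b. That does not happen in the b = 0.35 column, where g·r00 is at most 0.30.

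**Simulation.** N = 50, treatment group in every model, the last three rows above with κ = 0.5, 0.5 and 0.4 respectively. Evidence means a posterior probability of at least 95% under a flat prior. That threshold is an assumption: the plan sets 95% only for comparing groups at baseline. Selection means that only women with high Y0 are enrolled, as the entry criteria require in part.

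| | No selection | With selection |
|---|---|---|
| Raw difference, mean slope (true 0.35) | 0.03–0.09 | about 0.17 |
| Raw difference, path detected | 7–14% | 34–40% |
| True path zero: raw difference gives wrong-direction evidence (nominal 5%) | 15–31% | 7–11% |
| True path 0.35: the two permitted scores disagree | 53–67% | 42–45% |

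Across both columns, residual change detects the path in about 67–80% of trials and the fully adjusted model in about 76–86%. Repeat runs with different selection cuts moved these figures by a few percentage points.

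Selection softens the problem. It narrows the spread of Y0, so the g·r00 part shrinks and the slope moves towards b/2 = 0.175. The halving remains.

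**The case against.** **Only one of the two permitted options is affected.** True: residual change sits in the same sentence and does not carry the bias. But the plan permits either and gives no rule, so the exposure stands.

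**The result depends on what drives the outcome.** If follow-up PHQ-9 truly depends on raw change and not on the later level, the difference score is unbiased. Secondary Aim 1 is worded in terms of change, so this has some force. The plan does not argue for that model, and it also allows residual change.

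**The sizes rest on assumed correlations, and the plan does not favour yes/no testing.** This stands. The direction and the halving follow from the algebra; the percentages are illustrations.

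**Full adjustment gains little over residual change, and could overload the abstinence model.** Both parts have merit. In a further setting (κ = 0.5, r00 = 0.6, g = 0.3, b = 0.3, detection at t > 1.96) the two forms tied at 49%. For abstinence, the 7.6% and 25% rates in the SAP's simulated example give 25 × 0.076 + 25 × 0.25 ≈ 8 abstinent women, or about 2 per term with four terms. The fix is limited accordingly.

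**Stronger readings that the documents do not support.** A reader might infer that enrolling only depressed women makes the bias worse; the calculation shows the opposite. A reader might infer that the path generally reverses; the usual result is attenuation. A reader might want the same baseline terms in the structural model; nothing computed here bears on that model.

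**Conclusion.** The point holds for the raw difference-score option. No other section repairs step (c), because the general covariate rule is unlikely to bring in a minimization factor. If the outcome depends on the later mediator level, the raw difference at least halves the path. It shrinks it further where baseline depression is prognostic and correlated with the baseline mediator. A spurious wrong-signed slope is expected when the true path is null or g·r00 > b.

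Under the assumed correlations, a path of 0.35 is found in about 7–40% of trials (the higher values with selection), against about 67–80% for residual change. With a null path, wrong-direction evidence appears in about 7–11% of trials with selection and 15–31% without. The latter range applies if the assumed correlations are read as already holding among enrolled women. Abstinence was not simulated; the same argument carries over only if baseline affect or depression predicts abstinence.

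The stakes are modest: this is a conditional fallback for an exploratory secondary aim, and neither the feasibility benchmarks nor the rule for proceeding to a larger trial uses it. It is still worth correcting, because the change is small and removes a choice that could decide the aim's conclusion.

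**What to change.** Delete the raw difference-score option from step (c) and specify one model per outcome before the data are seen:

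- **PHQ-9:** 4½-month PHQ-9 on the follow-up mediator value, with baseline mediator, baseline PHQ-9 and treatment group as covariates.
- **Abstinence:** 4½-month abstinence on the residual change score and treatment group only, because events will be few.

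Name the visit that supplies the follow-up mediator value. Step (c) refers to six months, but the last scheduled visit is at 4½ months postpartum.

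The cost is a sentence or two of SAP wording and two extra terms in the PHQ-9 model. No new data are needed: PHQ-9, PANAS and the PROMIS cognitive scale are already scheduled at baseline and at the 4½-month visit.

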Timeline Follow-back Interview (TFBI)¹¹¹ Self-reports of smoking will be collected from participants in Aims 3 and 4 at baseline using the TFBI. Starting at study entry, self-reported smoking will be collected daily with the daily diary Ecological momentary assessments (EMA) through the Qualtrics platform. In the event the participant does not complete the EMA daily diary, smoking data will be collected at counseling visits.

Biochemical Abstinence Verification All participants who self-report as being abstinent at each treatment visit will be sent a urine test (cotinine or anabasine)to biochemically verify abstinence. Participants will be asked to send a picture of the urine test to the research staff via text message or email and/or return the urine samples via mail in the labeled box provided to them. This process is used in several of our smoking cessation studies and offers the patient a convenient way to verify smoking and to also provide remote biochemical verification of self-reported abstinence. We will use a urine cotinine test that measures nicotine at 100 ng/mL, with a negative result to verify abstinence. Abstinence Definitions Point-prevalence abstinence at the end of prenatal treatment and end of postpartum treatment and 4 ½ months postpartum follow-ups will be defined as both a self-report of not smoking during the previous 7 days and a negative result. Regarding the primary outcome of abstinence at 4.5 months postpartum, because the study will allow for a variable quit date through the postpartum period, we will consider quit attempts up to week 14 of the postpartum period, which will allow for the recommended 2-week grace period for prolonged abstinence prior to the postpartum end of treatment. Thus, prolonged abstinence at 4.5months postpartum will be defined as a self-report of not smoking from Week 16 through the 4.5-months postpartum follow-up and a negative result .

The PHQ-9¹¹⁹ will be used to assess depression outcomes. The PHQ-9 has been found to reliably measure response to depression treatment, including responsiveness to criterion standards for full, partial and remission of DSM-IV symptoms of major depression.¹²⁰

The GAD-7 will be used to asses anxiety outcomes. The GAD-7 is a validated, seven-item scale developed to assess the presence and severity of generalized anxiety disorder symptoms over the last two weeks. Empirically-derived cut-offs can be used to quantify severity of reported symptoms.

Treatment Mechanisms

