The PANAS¹²¹, a widely-used 10 item self-report measure of the experience of positive and negative affect within the past week, will be used in Secondary Aim 1 exploratory analyses of hypothesized BA mediators (PA and NA). It will be assessed at baseline and each counseling visit.

The PROMIS Cognitive Function-Abilities (CF-A) Short-form¹²² is from the Patient Reported Outcomes Measurement Information System. This 8-item scale assesses perceived cognitive deficits, including mental acuity, concentration, memory, and perceived changes in these cognitive functions and the extent to which cognitive impairments interfere with daily

functioning. It will be assessed at baseline and each counseling visit. It will be used in Secondary Aim 1 exploratory analyses of hypothesized BA mediators (*cognitive function*).

Nicotine Withdrawal

The Wisconsin Smoking Withdrawal Scale (WSWS)¹²³ This 28 item scale will be used to assess nicotine withdrawal symptoms.

Smoking cessation or depression treatment following enrollment

At each study visit, participants will be asked whether they have started any counseling or medications for the treatment of smoking or depression. These data will be used as covariates in analyses of outcome, as needed.

Additional Measures

Childhood Trauma questionnaire (CTQ). This is a standardized 28-item self-report inventory that measures the severity of five different types of childhood trauma. Approximately 5 minutes is required to complete the questionnaire. A 5-point likert scale is used for the responses from Never true to Very often true.

Medical History. This questionnaire assesses the participants current relevant medical history at the time of the baseline visit.

The Baseline Demographic and Smoking History Form. These questions expand on the data obtained during the pre-screening, providing more detailed information on demographics, information on smoking history (e.g., years smoked, current smoking rate, other nicotine/tobacco use) is also obtained. These questions have been used in our previous and current cessation studies to provide descriptive data for the study population.

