Mediational modeling will examine the degree to which putative mechanisms of behavioral change transmit the effects of the intervention on the specified outcomes. BSEM will investigate mediation of treatment effects by hypothesized mechanisms (positive and negative affect and cognitive deficits) utilizing MPlus v. 8.0.¹⁴⁴⁻¹⁴⁶ Measurement of positive and negative affect will use the PANAS. Measurement of cognitive deficits will use the CF-A. Models will evaluate whether change over time (captured using growth factors) in positive affect, negative affect and cognitive deficits, measured with the PANAS and CF-A, mediates the effect of treatment at six months post-partum. Examination of the posterior distribution of the indirect effects will evaluate the probability that mediational effects exist. For model simplicity it may be necessary to break these analyses into two distinct mediation models. However MCMC estimation has demonstrated superior small sample performance relative to maximum likelihood-based approaches in continuous, normally distributed data.^{147, 148} As discussed in the **Specific Data Analytic** section, minimal variability in growth factors representing change over

time, which may be partially a function of small sample size will result in use of an alternative approach.

Specific Data Analyses: Aim 4

The specific quantitative, analytic plan will focus on Primary Aim 4 and Secondary Aim 1.

Primary Aims

Aim 4 (Stage IB)

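### The fallback mediation step ends mediator change at a six-month visit that does not exist; if the 4½-month follow-up is meant, mediator and outcome share a visit and the link is only concurrent

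*Combined protocol and SAP*

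**What the plan says.** Under Specific Analyses: Secondary Aim 1 (Stage IB), the preferred analysis treats change in positive affect, negative affect and cognitive function as "mediators of treatment effects on 4 ½ month post-partum outcomes via structural equation modeling". If N = 50 gives too little variability in the slopes, three separate analyses replace it: a) mediator change over time by treatment, b) outcome by treatment, and c) outcome by mediator change. Step c) takes the outcome "as a function of change in the mediator captured either through a difference score" (six months minus baseline) or a "residual change score (six months residualized on baseline"). Treatment is not named as a term in step c).

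The mediation paragraph of Bayesian Modeling Strategy asks whether change in the mediators "mediates the effect of treatment at six months post-partum". It does not say which visits feed the growth factors.

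The Postpartum paragraph under Treatment gives one follow-up, at 4½ months, and this is the last column of Table 2. Treatment Mechanisms says of each mediator scale: "It will be assessed at baseline and each counseling visit". Table 2 also marks PANAS and PROMIS at the follow-up, where no counseling takes place.

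**The concern.** The theory in Scientific Premise runs from BA to affect and cognition, and from there to abstinence and mood. Testing it requires the mediator to be measured before the outcome. Step c) as worded uses a time point at which nothing is collected, so someone must reinterpret it before it can be run. The obvious reinterpretation, the 4½-month follow-up, puts the two measurements at one visit. A woman who is less depressed, or who has quit, may report better affect for that reason alone, and step c) would count this as support for the mechanism. At stake is whether Secondary Aim 1 says anything about direction.

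**Working it through.** The plan states no error rate, power or effect size for the mediation analysis, so there is no figure to reproduce. The check is timeline arithmetic, followed by an illustration under stated assumptions.

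**Timeline** (1 month = 30.4375/7 = 4.348 weeks, counted from birth)

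- End of postpartum treatment (PP4): a break of up to 1 month plus 4 visits over 6 weeks = 4.35 + 6 = 10.35 weeks. Compensation AIM 4 puts it at 2½ months = 10.87 weeks. The two agree closely.
- Outcome visit: 4.5 × 4.348 = 19.57 weeks. For depression: "Generalized linear modeling will evaluate depression, measured by the PHQ-9, at 4 ½ months postpartum as a function of treatment group". For prolonged abstinence: "self-report of not smoking from Week 16 through the 4.5-months postpartum follow-up", plus a negative test.
- Six months postpartum: 6 × 4.348 = 26.09 weeks, which is 26.09 − 19.57 = 6.52 weeks after the last visit.
- Six months from baseline, assuming delivery at 40 weeks: 26.09 − (40 − 18) = week 4.1 for entry at 18 weeks, and 26.09 − (40 − 32) = week 18.1 for entry at 32 weeks. No visit is tied to that point.
- PP4 to outcome: 19.57 − 10.87 = 8.70 to 19.57 − 10.35 = 9.22 weeks.
- Start of the abstinence window to follow-up: 19.57 − 16 = 3.57 weeks.

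A follow-up mediator reading therefore shares its visit with PHQ-9. The recall periods overlap (PANAS past week, PHQ-9 past two weeks), and the reading comes after the abstinence window has opened. A PP4 reading precedes both outcomes. The abstinence definition implies that postpartum treatment ends near Week 16 rather than at 2½ months. On that dating too, PP4 precedes the follow-up.

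**Illustration: N = 50, no mediator effect on the outcome, share of trials with p<0.05 for mediator change**

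Set-up A (4,000 runs per setting):

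- Baseline mediator m0 ~ N(0,1)
- PP4 mediator m1 = 0.6·m0 + 0.8·e
- Outcome y = −0.5·T + e
- Follow-up mediator m2 = 0.6·m1 + 0.8·e + c·y
- Model: y on T and mediator change

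| Path c | Change to follow-up | Change to PP4 |
|---|---|---|
| 0 | 5.5% | 5.2% |
| 0.3 | 44% | 5.0% |
| 0.5 | 84% | 4.6% |
| 0.8 | 99.6% | 5.1% |

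Set-up B lets depression persist between visits with autocorrelation ρ. Affect at each visit is c × depression at that visit + unit noise, and treatment lowers depression by 0.6 SD.

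- Change to follow-up, no other term in the model: at c = 0.3, 33% (ρ = 0) and 13% (ρ = 0.7). At c = 0.5, 64% and 27%.
- Change to PP4, with treatment and baseline PHQ-9: at c = 0.5, 10%, 14% and 15% for ρ = 0.3, 0.5 and 0.7. At c = 0.8, 16%, 27% and 31%.
- Adding PP4 PHQ-9 brings this back to about 5%. That follows from the set-up, because given depression at baseline and PP4, PP4 affect carries no further information on later depression.

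A further variant with concurrent affect driven by the outcome and a 0.6 SD treatment effect gave 61% (c = 0.3) and 98% (c = 0.5). Over paths of 0.3 to 0.5, the concurrent rate thus runs from about 13% to 98%.

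**The case against.** The case for leaving the plan alone has real weight. The analysis is exploratory, step c) is a fallback, and steps a) and b) do not depend on it. Feasibility is judged on retention and session completion, and progression on the relative risk of abstinence. The plan reports posterior probabilities, so no p<0.05 rule exists to be broken. All of this stands and limits the consequence. It does not supply a temporal order that step c) lacks, and the near-flat priors would not remove the bias.

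Some stronger readings are tempting but unsupported:

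- *The mediator is measured after the outcome.* In the Secondary Aim 1 section, six months has no anchor; the postpartum wording stands in Bayesian Modeling Strategy. The background on the earlier trial equates six months after treatment with about 4½ months postpartum, so a leftover label is more likely.
- *Reverse causation would satisfy step c) almost every time.* That holds only for strong assumed paths. The documents give no path, noise or stability value.
- *Moving the mediator to PP4 restores the nominal error rate.* This is true only if depression does not persist between visits, or if PP4 PHQ-9 is also in the model.
- *The mediation aim fails altogether.* The growth-factor model shares the problem only if its slopes include the follow-up, which the plan leaves open.

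**Conclusion.** The concern holds for the mediator-outcome link in the fallback, and for the growth-factor model if the follow-up is among its time points. As worded, step c) cannot be run. Under its most plausible reading it yields a concurrent association that cannot tell mediation from its reverse. The false-link rate is assumption-dependent, roughly 13% to 98% at N = 50 with outcome-to-affect paths of 0.3 to 0.5 and p<0.05 as a proxy; none of these is a figure for this trial. If Treatment Mechanisms rather than Table 2 governs collection, no follow-up mediator value exists and PP4 is the last one scheduled. Primary results are untouched. The point is worth correcting before analysis because data with a better time order are already scheduled.

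**What to change.** Change the wording in the mediation paragraph of Bayesian Modeling Strategy and in Specific Analyses: Secondary Aim 1:

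1. Replace six months with the 4½-month follow-up as the outcome time.
2. Define mediator change, and the growth factors in the mediation model, as baseline to PP4.
3. In step c) include treatment, baseline PHQ-9 and PP4 PHQ-9, or at least add a sensitivity model with PP4 PHQ-9.
4. Handle missing PP4 mediator values by the joint modelling already planned for non-smoking outcomes. Carrying the last treatment visit forward would mix prenatal and postpartum end points in a way that depends on dropout.
5. Report mediator change to follow-up only as a concurrent association.
6. Reconcile Treatment Mechanisms with Table 2 on whether the mediators are collected at follow-up.

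This is a cheap improvement: no new visit, no participant burden, analysis text only. It has costs. Mediator change between about 2½ and 4½ months is not used in the mediation test. Adjusting for PP4 PHQ-9 loses some precision and may absorb part of a true effect. The abstinence model will feel this most: at the plan's illustrative rates with 25 per arm, 0.076 × 25 + 0.25 × 25 = 1.9 + 6.25, or about 8 abstinent women. For that outcome the PP4 PHQ-9 term may fit better as the sensitivity model.
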